**REVISION HISTORY**

Revision #	Version Date	Summary of Changes	Consent Change?
1	10/28/19	Removal of fMRI Procedures	Y
2	2/4/20	Addition of follow-up assessment & clarify some procedures in Consent	Y
3	3/27/20	Adaptation of contingency plan in response to recent COVID-19 restrictions	Y

PROTOCOL TITLE:

## 1.0 Study Summary

Study Title	Feasibility Trial Assessing Adherence and Response to a Ketogenic Dietary Intervention for Individuals at High Risk for Alzheimer's Disease
Study Design	Intervention with pre- and post-assessments
Primary Objective	Assess ways to promote adherence & acceptability of ketogenic diet for individuals at high risk for Alzheimer's
Secondary Objective(s)	Assess neuropsychological, health, and functional outcomes in response to a 6-week ketogenic diet.
Research Intervention(s)	6-week group diet intervention
Study Population	Older adults aged, 60-75 (approximately)
Sample Size	N=10
Study Duration for individual participants	6-week intervention, and a maximum of 2 pre-intervention assessment meetings, 2 follow-up intervention assessments, and 1-month follow-up assessment.
Study Specific Abbreviations/ Definitions	EEG = electroencephalogram; APOE = apolipoprotein E; MNCD = Mild Neurocognitive Disorder; AD = Alzheimer's Disease

## 2.0 Objectives\*

**There is significant and growing evidence that adherence to a ketogenic diet may be an effective behavioral intervention for AD.** While previous studies have identified the basic mechanisms and interactions of a ketogenic diet with ApoE and lipid and glucose metabolism, feasibility testing in diverse human samples remains in the earliest phases of translational science. The current project will translate these findings into a new behavioral intervention to prevent AD using the *NIH ORBIT model* for early phase translational behavioral studies. This model includes Phase 1a: Define the Intervention, Phase 1b: Refine the Intervention, Phase 2a: Proof of Concept, and Phase 2b: Pilot Study. Phase 1a of this model (Defining the intervention) is underway. We have already recruited over 500 participants for the initial phase to identify a sample meeting our study criteria. Additionally, we have teamed with a community nurse practitioner to modify an existing ketogenic group intervention for application in research with older individuals. **The current study builds on both the basic science and existing feasibility trials to implement an intervention that would take into account genetics, neurophysiological correlates, and other psychosocial factors in a diverse, high risk older adult population. Especially important to the current application is the inclusion of neurophysiological assessment to identify neural correlates and improve assessment of intervention effects.**

### Measurement of Intervention effect and Identification of Neural Correlates

The existing literature suggests a link between the ApoE genotype and risk for AD—and further implicates a ketogenic diet in ameliorating this risk. One of the primary goals of the current study is to extend this work to neural measures linked to both ApoE genotype and ad in a diverse population. To this end, the current proposal involves the use of neuropsychological testing, electroencephalogram (EEG) to assess neurophysiological risk for ad and potential changes in neural measures post-intervention.

**Aim 1: Refine. Use a team science approach to optimize and develop a protocol to promote adherence to a 6-week ketogenic diet intervention in high risk older adults. We expect that the use of a team science and patient-driven approach will enhance adherence (80%) and retention (100%) in the Proof of Concept stage.**

**Aim 2: Proof of Concept. Assess the feasibility, acceptability, and preliminary effects of implementing a ketogenic dietary intervention for older adults at high risk for AD.** Participants, aged 60-75 (N=50), will complete in-person neuropsychological assessments to assess for MNCD status, and saliva samples will be collected to assess for ApoE genotype. We will recruit 10 participants (5/10 ApoE €4+) who meet criteria for MNCD to complete a feasibility study assessing adherence to a ketogenic diet. **Hypothesis 1: We expect that interdisciplinary collaboration and a patient-centered approach will increase acceptability to a ketogenic diet, as evidenced by an 80% dietary adherence rate. Hypothesis 2: We expect preliminary evidence that adherence to the ketogenic diet will improve cognitive performance on memory tasks, and the diet may have a greater impact on cognitive scores for ApoE €4+ participants.**

**Aim 3: Examine the intervention effect on neural correlates of AD and ApoE €4.** Participants selected for the intervention (N=10) will complete pre- and post-

PROTOCOL TITLE:

intervention EEG assessments to identify treatment effects. **Hypothesis 1: Ketogenic Diet will reduce P300 latency and increase P300 amplitude** **Hypothesis 2: The impact of the ketogenic diet on P300 latency and amplitude will be larger among ApoE  $\epsilon$ 4+ carriers.**

**COVID-19 Update:** Pre- intervention assessments have mostly been completed. Post-intervention EEG assessments have been suspended; however, if COVID-19 restrictions are lifted in time, post-intervention EEG, vitals, and blood-draw assessments will be completed according to original protocol. For the 1 participant who did not complete the pre-assessments, we will collect cognitive data over the phone and will not include EEG data.

**Aim 4:** We will examine whether variability in the p300 relates to cognitive measures, and if it better differentiates ApoE genotype and the impact of a ketogenic diet than cognitive measures. In conjunction with the in-person neuropsychological assessments and genotyping (n=50), we are proposing to add an EEG assessment at this phase to assess neural risk factors for ad. For this portion, we are interested in adding an additional 25 low-risk participants to the sample as a comparison group in order to identify and confirm neural correlates of MNCD and ApoE  $\epsilon$ 4 status. **Hypothesis 1: MNCD will have increased latency and reduced amplitude p300 relative to healthy controls.** **Hypothesis 2: among MNCD, ApoE  $\epsilon$ 4 genotype will be associated with increased latency and reduced amplitude p300.**

**COVID-19 Update:** All phase 2 in-person and EEG assessments were completed prior to recent restrictions and are not subject to change.

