### Pre-intervention Assessments:

All participants will complete two pre-intervention assessment appointments. These appointments will be scheduled within 2 weeks of the first intervention group meeting. This appointment will include: consenting, brief neuropsychological testing (*The Repeatable Battery for the Assessment of*

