**PROTOCOL TITLE:**

*Neuropsychological Status - RBANS), and the emotion battery of NIH toolbox.*  
The total meeting should last approximately 1 hour. These meetings will be completed by a clinical psychologist or a Ph.D. level clinical psychology graduate student.

The second visit will involve completing an EEG, which will involve picture and audio memory tasks. Each appointment will last approximately 1-hour. Participants will be compensated \$75 total for both appointments.

**COVID-19 Updates:** If in-person restrictions are lifted by the end of the six-week intervention, post-intervention EEG and follow-up assessments will be completed on an individual basis, while we continue to take necessary safety and hygiene precautions outlined in the original protocol. Neuropsychological assessments will be completed via telephone using a battery of pre-standardized assessments. Otherwise, the EEG post-intervention assessments will not be completed, and all assessments will be completed via HIPAA-compliant Zoom or telephone.

Given that all participants have already enrolled in the trial, we will also complete individuals calls to these participants to explain the changes in the protocol and to obtain verbal consent to continue in the study. We will test each participants capability to use the video conferencing software prior to the first group meeting.

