## **23.0 Resources Available**

We are proposing to recruit a total of 10 participants, with at least 5 being APOE 4+. Participants will be selected from eligible participants from a previous, related study who express interest in completing the dietary intervention. As part of an initial screening/recruitment study, we have surveyed over 500 participants. The next screening study will recruit a subsample of these individuals for neuropsychological testing and APOE sequencing. The current study will further select from this subsample.

The current PI will devote up to %50 time to conducting the current research study. The Center for Translational Behavioral Science is currently being equipped with a phlebotomy room, which will be used for health assessments and blood draws. We will also have a conference room equipped with video conferencing to complete the intervention. Participant rooms in the center will be used for completing assessments in a quiet environment. Our center will be sharing a space with [name] EEG lab, where the follow-up EEGs will occur.

Our team consists of multiple clinical psychologists, a nurse practitioner, Geriatrician M.D., geneticist, research methodologist, and a Ph.D. level registered dietician. These study personnel will be available for consultation in the case of any adverse event.

Our team has met multiple times to develop the current grant and after award to plan the project. A copy of this protocol will be shared with all key personnel.

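### Aim 3 reads uncontrolled P300 change as a treatment effect, while an earlier pre-diet EEG that probably exists for most or all diet participants has no stated role

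*Combined protocol and SAP*

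**What the plan says.** Under 2.0 Objectives, Aim 3 states: "Participants selected for the intervention (N=10) will complete pre- and post". The sentence goes on to name EEG assessments meant to identify treatment effects on P300 latency and amplitude. There is no control group.

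4.0 Procedures Involved puts the baseline EEG at the second pre-intervention appointment: "The second visit will involve completing an EEG, which will involve picture and audio memory tasks". On timing it says: "These appointments will be scheduled within 2 weeks of the first intervention group meeting". The on-diet EEG falls in the final two weeks of the diet. The 1-month follow-up lists cognitive and emotional testing and questions, but no EEG.

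The COVID-19 update to Aim 3 suspends the post-intervention EEGs unless restrictions lift in time. It reports the pre-intervention assessments as mostly done, with one exception: "For the 1 participant who did not complete the pre-assessments, we will collect cognitive data over the phone and will not include EEG data".

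The earlier n=50 neuropsychology and genotyping stage is covered by Aim 4, which says: "we are proposing to add an EEG assessment at this phase to assess neural risk factors for ad". Its COVID-19 update says: "All phase 2 in-person and EEG assessments were completed prior to recent restrictions and are not subject to change". On where the diet group comes from, 23.0 Resources Available says: "The current study will further select from this subsample".

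The only analysis text, in 15.0 Data Management and Confidentiality, names descriptive and correlational analyses, with regression, ANOVA and t-tests as options. No section gives the phase 2 EEG a role in Aim 3.

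**The concern.** With one recording before the diet and one during it, a P300 change could come from the diet, from repeating the task, from the course of mild neurocognitive disorder (MNCD), or from ordinary variation between visits. Nothing in the Aim 3 comparison separates these. The Background section nevertheless says that a confirmed result would supply mechanistic evidence for P300 as a target of the diet.

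If the diet participants also had a phase 2 EEG, the change from that recording to the pre-intervention EEG is P300 movement in the same people without the diet. It would give readers a yardstick for the on-diet change, and it has already been collected. The same recording could serve as a baseline for the one participant now left out of the EEG data.

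**Working it through.** The plan states no power, alpha, effect size or SD for P300, and N=10 is a feasibility number (10.0 Local Number of Subjects). There is no figure to reproduce.

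**Are there two separate pre-diet EEGs?**
- Phase 2 EEGs are reported as all completed. Pre-intervention assessments are only mostly completed, with one person missing. These cannot be the same set of recordings.
- Phase 2 is not defined in that update. It cannot mean the diet stage, because that stage's post-intervention EEGs are suspended. It fits the n=50 stage that Aim 4 describes.
- Aim 2, the screening text in 4.0 and section 23.0 all draw the diet group from the people tested and genotyped at that stage.
- It follows that most or all diet participants probably have a phase 2 EEG. This is inference. Section 23.0 describes the feeder study without naming EEG, and no section lists recordings by person.

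**Counts.** Pre-post EEG pairs under the plan: 10 − 1 = 9 at most. People with two pre-diet EEGs: up to 9. Pairs if the tenth participant has a usable phase 2 EEG and a post-intervention EEG: 10.

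**What the tenth pair adds.** The 95% CI half-width, in SDs of change, is t(0.975, n−1)/√n.
- n=9: 2.306/3 = 0.77.
- n=10: 2.262/3.162 = 0.72.

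For the ApoE comparison (Aim 3, Hypothesis 2), the groups go from 4 v 5 to 5 v 5. The difference detectable with 80% power (exact two-sample t-test, two-sided 5%) falls from 2.19 to 2.02 SD of change.

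**Why a no-diet interval matters.** Assume no diet effect, a retest shift of g P300 SDs, equal SDs, and correlation r between recordings. The SD of change is √(2(1−r)), so the noncentrality for 9 pairs is 3g/√(2(1−r)). The shift sizes and r are assumptions. The rejection rate of a two-sided 5% paired t-test is:

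| g | r = 0.5 | r = 0.9 |
|---|---|---|
| 0.2 | 8% | 22% |
| 0.3 | 12.5% | 42.5% |

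**Cost of a formal contrast.** On-diet change minus no-diet change is post − 2×pre + phase 2. With equal correlations its variance is (1+4+1)(1−r) = 6(1−r), against 2(1−r) for simple pre-post change. The SE ratio is √3 = 1.73. With 9 people at r=0.5, the half-width is 1.33 P300 SDs instead of 0.77. At r=0.9 it is 0.60 instead of 0.34.

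**The case against.** The strongest objection is that the earlier EEGs are inferred. Saying that a phase is finished does not show that each of these ten people has a usable recording, and the exclusion of the tenth participant would also fit a person with none. This stands, and it is why the fix begins with a check by study ID.

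Second, the interval is a weak control. It starts at the visit whose testing established MNCD and so eligibility. Aim 4 expects P300 to track MNCD, so regression to the mean could move P300 over that interval and not over the next. The length of the interval is not given, and the phase 2 EEG task is not described. This also stands. It limits the comparison to a descriptive one.

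Three stronger readings are tempting.
- A reader might infer that a diet effect should be claimed only for change beyond the no-diet change. The documents do not support that as a rule: its SE is 1.73 times larger, and its reference interval begins at selection.
- A reader might infer a gain in precision from averaging two pre-diet EEGs. Under equal correlations the SE would be √(1.5/2) = 0.87 of its single-baseline value, or 13% smaller. But averaging assumes no trend between the two recordings. Whether there is one is the open question, and nine people cannot show its absence.
- A reader might infer that the plan discards an existing recording or rules out its use. No pre-intervention EEG was recorded for that participant, and on using phase 2 EEGs in Aim 3 the plan is silent.

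Finally, P300 is a secondary outcome of a feasibility study, and the post-intervention EEGs may never happen. That limits the weight of the point. It does not remove it while Aim 3 still speaks of treatment effects.

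**Conclusion.** The point holds in a limited form. Aim 3 attributes uncontrolled P300 change to the diet. An earlier pre-diet EEG that probably exists for this group is given no role, either as a no-diet interval or as a substitute baseline. At stake are a descriptive no-diet comparison in up to 9 people and a possible tenth pair (half-width 0.77 to 0.72 SD of change). The main benefit is to interpretation; the gain in precision is small.

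This rests on assumptions that the documents do not settle: that the phase 2 EEGs exist for these individuals, that task and set-up match, and that post-intervention EEGs are recorded. Without post-intervention EEGs there is no Aim 3 contrast, though the two pre-diet recordings would still give P300 retest reliability for planning the next study.

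**What to change.** Before any post-intervention P300 data are examined, add a short paragraph to Aim 3 covering four steps.

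1. Check by study ID whether each diet participant has a phase 2 EEG with the same task and recording set-up, and state the number who do.
2. For those people, report the phase 2 to pre-intervention change (no diet, up to 9 people) beside the pre-intervention to week 5-6 change, with the dates of all recordings. Keep this descriptive; do not test the difference between the two changes as a decision rule.
3. Where the no-diet change is of similar size to the on-diet change, word the P300 result as uncontrolled change and not as a diet effect.
4. Replace the blanket EEG exclusion in the COVID-19 update. If the tenth participant has a comparable phase 2 EEG and a post-intervention EEG, use the phase 2 EEG as a flagged baseline and show results with and without that person.

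The cost is linking existing files and writing one paragraph; no new visits or recordings are needed beyond those already planned. The write-up should state the limits: the intervals may differ in length, the first begins at the selection visit, and the comparison is possible only if the suspended EEGs go ahead.

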## 1.0      Background\*

**AD is the sixth leading cause of death in the United States, and minority older adults are disproportionately affected by such neurocognitive disorders.** For example, the Alzheimer's Association reports that African Americans are twice as likely to develop AD, while Hispanic Americans are approximately one and a half times more likely compared to Caucasians. Existing research demonstrates that genetic risks such as the apolipoprotein E (ApoE)  $\epsilon$ 4 allele may be a significant contributor to this discrepancy, due to higher rates in certain minority groups. In addition to increased genetic risk, minority individuals may also be more likely to experience sociocultural risk factors, such as reduced access and poorer quality of health care, lower quality of education, and increased chronic environmental and psychosocial stressors. Combined, the literature demonstrates that aging African Americans and other minority groups may be at the greatest risk for being diagnosed with a neurocognitive disorder, but have been disproportionately neglected in research. Despite this underrepresentation, basic science, as well as large epidemiological studies over the past several decades have illuminated a wide range of risk and resiliency factors for late-life cognitive decline for both minority and Caucasian populations.

For example, it is well accepted that **carriers of an ApoE  $\epsilon$ 4 allele, compared to carriers of  $\epsilon$ 2 and  $\epsilon$ 3 alleles, are at the greatest risk for developing AD;** yet, having an ApoE  $\epsilon$ 4 allele is not sufficient to develop AD. The expression of this genetic risk is

PROTOCOL TITLE:

influenced by a wide range of environmental risk factors, ranging from stressful life events to diet and exercise. **A ketogenic diet, in particular, holds promise for addressing deficiencies linked to the ApoE ε4 allele.**

ApoE is involved in lipid metabolism, and the ApoE ε4 allele is not as efficient as other variants; thus, researchers have indicated that genotype should be taken into account when applying a dietary intervention for AD. In addition to lipid metabolism, glucose metabolism may be another contributor to neurodegeneration due to decreasing metabolic efficiency with age. For example, researchers have demonstrated that a high-glycemic diet (e.g., high sugar/carbohydrate) is associated with accumulation of amyloid plaques in cognitively normal adults. A diet high in healthy fats and low in carbohydrates (i.e., ketogenic) induces the creation of ketone bodies, which can be processed by the brain in place of glucose. Further, ketone supplements, specifically, appear to improve cognitive functioning, even when a normal diet is maintained. The effect, however, is weakened in individuals with an ApoE ε4 allele; ketone supplements do not account for the potential benefits of healthy fats and reduced carbohydrate intake on APOE functioning – an effect only diet change may produce. **The ketogenic diet shows promise in addressing problems in lipid metabolism and may circumvent inefficient glucose metabolism**, which indicates diet as a potent therapeutic intervention for cognitive functioning. The ketogenic diet has already proven a powerful therapeutic tool in pharmacoresistant epilepsy and is being studied for its effect on tumor growth in cancer.

Less attention has been given to the potential therapeutic effects of a ketogenic diet in individuals with mild neurocognitive disorder (MNCD) and AD. A small feasibility study demonstrated that the ketogenic diet can successfully improve cognitive scores in older adults with mild AD (N=10 completers) across a 3-month span, although all four patients with moderate AD dropped out before completing the trial. Additionally, ketone supplements to a normal diet have shown small, but positive effects in improving cognitive functioning scores in individuals with AD without an ApoE ε4 allele. These findings demonstrate that ketosis is generally beneficial and such a trial is feasible; however, implementation may be challenging in patients who are already diagnosed with AD. Further, given the evidence of an interaction between ApoE and ketone bodies, feasibility studies and future clinical trials should experimentally assess the cognitive effects and neural correlates associated with a ketogenic diet in humans.

**In sum, there is significant and growing evidence that adherence to a ketogenic diet may be an effective behavioral intervention for AD.** While previous studies have identified the basic mechanisms and interactions of a ketogenic diet with ApoE and lipid and glucose metabolism, feasibility testing in diverse human samples remains in the earliest phases of translational science. The current project will translate these findings into a new behavioral intervention to prevent AD using the *NIH ORBIT model* for early phase translational behavioral studies. This model includes Phase 1a: Define the Intervention, Phase 1b: Refine the Intervention, Phase 2a: Proof of Concept, and Phase 2b: Pilot Study. Phase 1a of this model (Defining the intervention) is underway. We have already recruited over 300 participants for the initial phase to identify a sample meeting our study criteria. Additionally, we have teamed with a community clinic to modify an existing ketogenic group intervention for application in research with older individuals. **The current study builds on both the basic science and existing**

PROTOCOL TITLE:

**feasibility trials to implement an intervention that would take into account genetics, neurophysiological correlates, and other psychosocial factors in a diverse, high risk older adult population. Especially important to the current application is the inclusion of neurophysiological assessment to identify neural correlates and improve assessment of intervention effects.**

